## 5.2. Randomization

The sampling method will be non-probability consecutive sampling. Randomization was conducted using random numbers obtained from statistical analysis tool EPIDAT (Epidat: Version 4.2, July 2016. Consellería de Sanidade, Xunta de Galicia, España; Organización Panamericana de la Salud (OPS-OMS); Universidad CES, Colombia. Available at: <http://www.sergas.es/Saude-publica/EPIDAT>). Patients will be recruited the day before the surgery, they will be informed about the trial and informed consent will be obtained. To prevent bias, randomization list will be guarded by the clinical trial unit. The anesthesiologist will call the clinical trial unit to obtain the randomization sequence when a patient is selected and the arterial line is placed.

## 5.3. Description of the trial treatments

Two groups:

- Arm A: Conventional hemodynamic management
- Arm B: Goal-directed therapy

### Anesthetic protocol

1. Basic Anesthetic Monitoring: EKG, BP, SpO2.
2. Placement of peripheral venous line on the opposite arm of the surgery. 16 gauge if possible.
3. Administration of midazolam 2 mg IV if necessary.
4. Thoracic epidural catheter placement: T2-T6.
5. Biespectral index sensor placement.
6. Placement of **TOF-Watch** monitoring.

7. Induction:
  - Fentanyl 2 mcg/Kg IV.
  - Propofol 2 mg/Kg IV.
  - Rocuronium 0,6 mg/Kg, after calibration of TOF-Watch monitor.
8. Orotracheal intubation. Comprobatation of correct placement of double lumen endotracheal tube with flexible bronchoscopy. Bladder catheterization.
9. Mechanical Ventilation, volume control. Tidal volume 8 ml/kg ideal weight, respiratory rate 12-14 breaths per minute. FiO2 40% and positive end-expiratory pressure 5 cm H2O.
10. Sevoflurane for maintenance of general anesthesia, BIS objective between 40 and 60.
11. **Antibiotic prophylaxis** (Cefazolin 2g IV). We repeat cefazolin 2 g three hours after the beginning of the surgery.
12. Placement of an arterial line on the radial artery of the opposite arm of the surgery. Invasive arterial blood pressure monitoring (FloTrac system). Obtaining baseline VSI and CI value. ARTERIAL BLOOD GAS SAMPLING (induction) AND LABORATORY BLOOD TEST (creatinine), ev1000 clinical platform (hemodynamic data collection).
13. **RANDOMIZATION (trial treatment)**, Clinical Trial Unit, HUVR.
14. Central venous catheterization of the internal jugular or subclavian vein of the side of the surgery. VENOUS BLOOD GAS SAMPLING (induction).
15. Placement in lateral decubitus position. Inflation of the bronchial balloon of the double lumen tube after verification with fiberoptic bronchoscopy. Placement of thermal blanket.
16. Alveolar recruitment maneuver in bipulmonary ventilation: With pressure controlled ventilation, we set the inspiratory time at 50%, and we establish the respiratory rate at 12 rpm. The pressure over PEEP (Positive End-Expiratory Pressure) is kept constant at 20 cm H2O. The inspiratory pressure and the PEEP increase simultaneously and progressively from 30/10 to 35/15 and finally to 40/20 cmH2O. This last 40/20 cmH2O recruitment pressure is maintained for 10 cycles. Subsequently, the PEEP decreases gradually, returning to the baseline parameters, maintaining the PEEP at 7 cmH2O. After performing the recruitment maneuver, we return to volume controlled ventilation.
17. Begin unipulmonar ventilation. VT 4-6 ml / kg ideal weight. Start FiO2 at 80%, and progressively reduce to 50%, once stable SpO2 above 90% is achieved. PEEP 7 cm H2O. Respiratory rate that avoids auto-PEEP and aiming at PaCO2 values between 40 and 60 mm Hg (permissive hypercapnia). Airway peak pressures below 30 cm H2O. Alveolar recruitment in unipulmonar ventilation if necessary.
18. Epidural bolus of 5-7 ml of bupivacaine 0.1% plus fentanyl 5 mcg/ml.

**19. START OF SURGERY.**

20. ARTERIAL AND VENOUS BLOOD GAS SAMPLING (OLV-20 min). ev1000 clinical platform (hemodynamic data collection)

**21. Anesthetic Maintenance:**

- Sevoflurane, bispectral index between 40-60.
- Remifentanil, 0.03-0.05 mcg/kg/min.
- Fluid and hemodynamic therapy according to allocation group.
- **Rocuronium 5 mcg/Kg/min until 30 minutes before the estimated time to the end of the**

**surgery.** TOF control every 45 minutes, seeking to maintain TOF < 3 signs.

- Epidural continuous perfusion: bupivacaine 0.1% plus fentanyl 1 mcg/ml 5-7 ml/h. Begin 60 minutes after the initial bolus.

**22. 30 minutes before the estimated time to the end of the surgery:**

- Stop continuous perfusion of rocuronium.
- Paracetamol 1 g (acetaminophen) or dipyrone 2 g IV.
- Antiemetics: Ondansetron 4 mg IV (assess the risk of PONV, in case of high risk add 4 mg of Dexamethasone IV in the induction).

23. ARTERIAL AND VENOUS BLOOD GAS SAMPLING (End of surgery). ev1000 clinical platform (hemodynamic data collection)

**24. Emergence:**

- Reversion of neuromuscular block:
  - + If TOF < 3 signs, administer sugammadex 4 mg/Kg IV.
  - + If TOF  $\geq$  3 signs or  $T_4/T_1$  ratio < 0.9, administer sugammadex 2 mg/Kg IV.
- **Extubation** when  $T_4/T_1$  ratio > 0.9 and satisfactory spontaneous ventilation.

[figure not shown]
**Arm A: Conventional hemodynamic management**

On the basis of a continuous infusion of 2 ml/kg/h of balanced crystalloid solution (restrictive fluid therapy), the clinician will try to get basic intraoperative hemodynamic objectives: Heart rate 60-100 beats per minute, mean arterial pressure 65 mm Hg, serum lactate 2 mmol / L, oxygen saturation 95% (90% during one lung ventilation). The use of fluids and vasoactive agents will be at the discretion of the operating room anesthesiologist. The total of fluids administered in the intraoperative period will be fixed in a maximum of 2000 ml of crystalloid solutions.

**Arm B: Goal directed therapy**

[figure not shown]
The hemodynamic algorithm will be based on systolic volume index and fluid challenges. FloTrac sensor (this sensor connects to any existing arterial catheter and provides advanced hemodynamic parameters through pulse contour analysis) and EV1000 clinical platform (clinical platform from Edwards Lifesciences that provides advanced hemodynamic monitoring) will be used to calculate cardiac index and systolic volume index. The goal directed therapy target value is a cardiac index equal or superior to 2.2 l/min/m^2.

3 steps:

\*\* Bolus is administered until IC  $\geq$  2.5 l / min / m^2 or SVI increase is  $<$  10%.

- Step 2: ¿Mean Arterial Pressure (MAP)  $\geq$  65 mm Hg?

- Step 3: Reevaluate steps 1 and 2 every 10 minutes. In all cases, supplementary fluids will be administered to replace blood loss. RBC concentrates will be transfused to maintain hemoglobin above 8 g/dl. If coagulopathy is suspected, it will be corrected according to rotational thromboelastometry.

#### **5.4. Procedures of the study and treatment duration**

Patients undergoing thoracic surgery will have a preanesthesia evaluation. Once the surgical programming of the week is published, the inclusion criteria and the absence of exclusion criteria will be checked. We are going to compare two interventions: the use of goal-directed therapy versus conventional hemodynamic management.

The anesthetic technique will be the same in both groups, as well as the invasive techniques used (epidural, double lumen tube placement, arterial route, central line). The intervention finishes when the patient is extubated in the operating room, so both groups of patients will receive the same treatment in the postoperative period.

The patient will undergo daily clinical follow-up during the admission to monitor the appearance of complications, as well as to check the survival at first month. The detailed schedule of procedures is included in section 7.

#### **5.5. Masking**

The patient, investigators, surgeons and physicians responsible for postoperative care will be unaware of the treatment assigned. The anesthesiologist responsible for the patient in the intraoperative period will know the assigned intervention. All patients will be monitored as is protocolized in this type of surgery: invasive arterial pressure through a radial arterial catheter and central venous pressure through a central venous line in the subclavian or jugular vein. Through the FloTrac sensor, the information from the artery wave is transmitted to the EV1000 monitor, allowing us to have real time information about advanced hemodynamic values such as the cardiac index or the systolic volume index. Another investigator (not the operating room anesthesiologist) will collect the intra and postoperative data.

In the conventional hemodynamic management group, the anesthesiologist will not have access to the advanced hemodynamic data of the EV1000 monitor, but will have access to conventional monitoring data and analytical data, which are part of our routine management. For this reason, the ev1000 monitor will be covered with an opaque material.

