This study is designed to quantify and compare the hemodynamic control of cardiac index in patients who receive either goal-directed therapy or conventional hemodynamic management in lung resection surgery. With the help of the ev1000 clinical platform, we will analyze the percentage of the intraoperative time in which the cardiac index is equal or superior to 2.2 l/min/m^2 (%). At the date of the elaboration of the study, this aspect has never been evaluated before, so we are going to conduct a pilot clinical trial.

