#### Procedure for notification of SAE/pregnancies (appendix I)

In the event of an SAE or a pregnancy case is collected, a member of the investigating team will complete and sign the notification form and will send it, by fax, immediately and always within 24 hours after having knowledge of the event to: [contact].

The CTU staff will review the form received and, if necessary, will request additional information from the investigator. When additional information is obtained, or it is resolved or unlikely to change, a follow-up report must be completed and faxed to the CTU. If there is a suspicion of a SUSAR, the investigator must provide the follow-up information requested by the CTU. Any SAE occurring more than 30 days after the end of treatment (without a time limit) should be reported if the investigator considers AAG to be related to the study treatment (i.e, if it is a serious adverse reaction) or if it is medically important.

It is not necessary to notify the CTU of the following SAE:

- Hospitalization or death due to the progression of haematological disease.
- Hospitalization for the performance of scheduled tests.
- Hospitalization to administer the study drug or to provide palliative care, terminal care or to perform scheduled surgical interventions.
- Hospitalization or prolongation of hospitalization to perform a procedure required by the protocol.
- Hospitalization or prolongation of hospitalization as a part of the routine procedure of the centre (for example, removal of a stent after surgery)

They will be collected in the CRF and in the patient's medical history.

Expedited notification of SUSARS to Health Authorities: The CTU will be responsible for notifying all the SUSARS collected in the study to the AEMPS, to the CEICs and to the Health Authorities, following the procedure indicated in the current legislation.

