### **11.3. Quality of data**

There will be an exhaustive control of the data quality. CRF will be reviewed by the person in charge of monitoring. Investigators will fulfill the CRF, not knowing the the assigned treatment. Patients data will be exported to a SPSS database.

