#### **14.2. RESOURCES AVAILABLE FOR THE REALIZATION OF THE CLINICAL TRIAL:**

The selection, intervention and follow-up of patients will be carried out in: Conventional hospitalization of thoracic surgery, surgery room No. 54 and Post-anesthetic Recovery Unit of the General Hospital Virgen del Rocío. We will have the usual team of surgeons and nurses. There will be an anesthesiologist who will anesthetize all cases to avoid interindividual variability.

For the supervision of the investigation methodology and statistical analysis, we will have the advice of [name] [name], from to the Research Support Unit of the Virgen del Rocío University Hospital (HUVR), together with Dra. [name], from the Clinical Trial Unit of the HUVR.

The staff of the Clinical Trial Unit of the HUVR, will make the request of the clinical trial to the Clinical

Research Andalusian Central Ethics Review Committee, to the CEI of the University Hospitals Virgen Macarena and Virgen del Rocío and will be in charge of the coordination of the project. The assigned personnel will be responsible for the maintenance of the file and the documentation of the trial. A monitoring plan will be made and it will be ensured that the collected data correspond to the source documents and that the procedures indicated in the approved protocol are followed. The staff of the clinical research and clinical trials unit of the HUVR will be responsible for expeditious notification of serious or unexpected adverse events.

4. INVESTIGATION MEDICINAL PRODUCT/DEVICE (Indicate the treatment(s) assigned to the subject after randomization)							
If more space is needed, use copies of this page and tick this box 							
Medicinal product	Dosage and units	Frequency	Route	Start date (dd-mmm-yyyy)	End date (dd-mmm-yyyy) (If this continues, tick this box)	Causal relationship	
						 Related  Not related	
						 Related  Not related	
						 Related  Not related	

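### The stated masking of investigators and surgeons is not secured by the written procedures: the EV1000 cover is described for one arm only, and the SAE form asks an investigator for the assigned arm

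*Combined protocol and SAP*

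**What the plan says.** Section 5.5 (Masking) states: "The patient, investigators, surgeons and physicians responsible for postoperative care will be unaware of the treatment assigned". It names the anesthesiologist in charge during surgery as the person who knows the assignment. Section 11.3 adds: "Investigators will fulfill the CRF, not knowing the the assigned treatment". Section 14.1 calls the trial blinded, and 10.3 lists only the clinician carrying out the procedure as impossible to blind.

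On the monitor, 5.5 explains that in the conventional arm the anesthesiologist must not see the advanced hemodynamic values, and continues: "For this reason, the ev1000 monitor will be covered with an opaque material". On data collection it says: "Another investigator (not the operating room anesthesiologist) will collect the intra and postoperative data".

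In Arm B (section 5.3) the algorithm runs on cardiac index and stroke volume index from the EV1000, with the instruction "Reevaluate steps 1 and 2 every 10 minutes".

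For serious adverse events, the notification procedure in section 9.3 says that "a member of the investigating team will complete and sign the notification form". Item 4 of that form (Appendix I) reads: "Indicate the treatment(s) assigned to the subject after randomization". Its last column, on the same row, is a Related / Not related box.

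**The concern.** A reader of 5.5, 11.3 and 14.1 would take it that everyone except the theatre anesthesiologist is masked. Two written procedures work against that. One makes the monitor look different in the two arms. The other asks an investigator to write down the arm while causality is being recorded.

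At stake are assessments that need judgement. The Berlin definition in 5.1 asks whether respiratory failure is explained by cardiac failure or fluid overload, and whether opacities on imaging are explained by other findings. In a trial of fluid and hemodynamic management, knowing the arm could colour the first of these in particular. Also at stake are the causality judgements that feed expedited reporting, and the accuracy of the blinding claim itself.

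**Working it through.** The plan gives no figure on this point, so there is nothing to recalculate. The check sets the masking statement beside each procedure that bears on it.

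1. **Monitor appearance by arm.** Conventional arm: covered (5.5). Arm B: no cover, screen or sham is described, and the anesthesiologist has to read the values and return to them every 10 minutes (5.3). Cover status therefore differs by arm and is informative to anyone who can see the monitor.

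2. **Timing.** The anesthetic protocol in 5.3 places randomization at item 13. EV1000 data collection is listed at item 12 (before it) and at items 20 and 23 (20 minutes into one-lung ventilation, and end of surgery). The last two fall in theatre after allocation.

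3. **Who collects.** Section 5.5 gives intraoperative and postoperative data to one investigator, a member of the group declared masked. If the readings are taken at the monitor, that person sees the cover status and then goes on to collect postoperative outcomes. If they are exported later, the exposure can be avoided. Section 3 says "With the help of the ev1000 clinical platform, we will analyze the percentage of the intraoperative time", and a time-based outcome makes stored data plausible, but no section states that data are exported or who extracts them.

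4. **SAE form.** The person completing item 4 is either masked or not.
   - If masked, as 5.5 and 11.3 say of investigators, item 4 cannot be completed without unmasking.
   - If not masked, the blanket statement about investigators is untrue for that person.

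   Either way, nothing in the visible text keeps the arm entry from the person judging causality. Section 9.2 gives that determination to the principal investigator or a designee. Nothing bars the anesthesiologist, who treats all cases (14.2) and knows each assignment (5.5), from that role.

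5. **Existing safeguards.** The clinical trial unit holds the randomization list (5.2), which protects concealment before allocation but not masking afterwards. A collector separate from the anesthesiologist (5.5) helps only if that collector does not see the cover status. Section 11.3 asserts masked completion of the CRF without giving a means.

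6. **Which results are exposed.**
   - Little affected: the primary outcome (device-derived), laboratory values, mortality, and adverse event counts (9.3.1 requires every event to be recorded whether or not it is related).
   - Exposed: judgement-based outcomes assessed by the collector, for example the origin-of-edema and imaging items of ARDS.
   - Exposed, only in patients with an SAE: causality judgements used for expedited reporting.
   - Hospital stay: exposed only if those who decide on discharge learn the arm, and nothing in the plan shows that they do.

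**The case against.** The strongest reply is that the monitor route is conditional. It needs surgeons with a line of sight, or a collector working at the screen, and the documents settle neither. The cover does what 5.5 says it is for: it withholds the values from the control-arm anesthesiologist. The SAE form is a generic medicinal-product template used in a non-pharmacological trial. Only the text from item 4 onward is available, so a separation described in its opening items cannot be excluded. Section 9.3.1 also has a safety medical monitor assess SUSARs. ARDS has timing and PaO2/FiO2 criteria that leave less room for judgement. Section 5.4 states the same postoperative treatment in both groups, and 10.3 says that the study is not powered for major complications.

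Most of this stands as a limit on size. It does not restore the masking statement. Collection in theatre after allocation is scheduled, no export is described, and item 4 as printed conflicts with investigators being unaware.

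Stronger readings are tempting and not supported:
- A reader might infer that staff were in fact unmasked. The documents show only that masking is not secured on paper.
- A reader might infer that the primary comparison is biased by assessors. It rests on device-recorded cardiac index.
- A reader might infer that the comparison of adverse events is distorted through causality. No between-arm outcome of related events is declared, and the safety analysis (10.5) takes all randomized patients.

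**Conclusion.** The point holds as a gap between a stated property and the procedures meant to provide it. Sections 5.5, 11.3 and 14.1 claim more masking than the plan secures, and 10.3 concedes too little.

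No size of bias is claimed, and none can be derived: section 10.1 sets 30 patients, 15 per arm, without event rates, effect size or SD. The scope is narrow, namely judgement-based secondary outcomes and causality for expedited reporting.

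The monitor part assumes that some surgeons, or the collector, can see the screen. The form part assumes that the unseen opening items contain no separation of the arm entry. Neither part calls the primary result into question. The gap is worth correcting because the remedy is cheap and readers would otherwise overrate the blinding.

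**What to change.** (a) **Monitor.** Make the EV1000 screen look the same to others in theatre in both arms, for example with an identical outer shield, leaving the anesthesiologist's access as each arm now requires. Obtain the data by coded export after surgery, so that the collector of postoperative outcomes does not see the cover status.

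(b) **SAE form.** Have the clinical trial unit, which already holds the list and receives the form, complete the arm field after the investigator has recorded causality. State that causality is not judged by the theatre anesthesiologist. (Section 9.2 names both the sponsor and the principal investigator in connection with causality; that is a separate, minor point to reconcile.)

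(c) **Wording.** The anesthesiologist's different use of the screen may still reveal the arm in theatre. So limit the masking statements in 5.5, 11.3 and 14.1 to roles that can be kept masked: patient, postoperative physicians, outcome collector and causality assessor. List surgeons and other theatre staff as possibly unmasked in 10.3. If (a) or (b) is not adopted, narrow the statements further to match.

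The cost is protocol and form wording, a shield used in both arms, and minor data-handling work. The downside is a less favourable masking statement. Clinical management is unchanged.

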## 6. SELECTION AND WITHDRAWAL OF PATIENTS

### 6.1. Inclusion criteria

- Adults patients (18 years old)
- Written informed consent
- Elective lung resection surgery (open or thoracoscopic lung lobectomy)

### 6.2. Exclusion criteria

- Severe obesity
- Moderate to severe aortic insufficiency
- Renal failure requiring hemodialysis
- Left ventricle ejection fraction less than 35 %
- Urgent surgery
- Patient in critical care unit or a patient who will be transferred postoperatively to the critical care unit.
- Participation in another study that could interfere in the three months prior to the start of this study.

### 6.3. Criteria for withdrawal of patients

The patient can withdraw his consent to be included in the study at any time without explaining the reasons. The patient should withdraw from the study when:

- The subject requests to withdraw from the study or withdraw informed consent.
- The investigator considers that withdrawal is the best option for the patient, particularly in case of an adverse or intolerable event.
  - Situation of hemodynamic instability of cardiological cause or massive hemorrhage that forces to increase the level of monitoring.
  - Need to transfer to intensive care unit (ICU).

Follow-up of patients withdrawn from the study: If a patient is removed prematurely from the trial, the main reason for the suspension will be provided and, as indicated by the PCB rules, the usual procedures for the treatment of the pathology will continue.

Premature termination of the study: Premature termination of the clinical trial may occur by a decision of the regulatory authorities, for a change in the opinion of the Ethics Committee, for safety and/or treatment problems or indications of inefficiency. The sponsor reserves the right to interrupt the study in any time for reasonable medical and/or administrative reasons.

